5.4.5.2 Laboratory values of special interest

Neutropenia, thrombocytopenia and leukopenia

Episodes of low neutrophil, platelets and WBC counts are of special interest. Episodes with CTCAE grade 3 and 4 and CTCAE grade 4 lasting 7 or more days will be analyzed.

An episode of e.g. low neutrophils starts with the first occurrence of a CTCAE grade ≥ 3 and lasts until the first time the CTCAE grade falls back to ≤ 2 .

In case the episode starts during EOT or Follow-up, the duration of this episode is defined to be missing. The reason for this approach is that after EOT laboratory data is only captured infrequently and therefore the duration of an episode would be overestimated due to lack of data.

If the episode starts before EOT and the CTCAE grade of the respective parameter does not fall back to grade ≤ 2 and the patient dies, the end of the episode is defined by the date of death. If the episode starts before EOT and lasts during Follow-up the episode is censored with the date of DBL.

Hepatic enzyme elevations (potential Hy's law cases)

Special attention will be paid to patients fulfilling the criteria for potential Hy's law cases. These are defined as those cases where a combination of all of the following events occurred: any on-treatment value of ALT and/or AST > 3 times upper limit of normal (3 x ULN) with total bilirubin \ge 2 x ULN and ALKP < 2 x ULN. The events can occur in any order, but must occur within 14 days of the previous event, i.e. the second event must occur within 14 days of the first event, and the third event must occur within 14 days of the second event.

Possible clinically significant abnormal lab values

Possible clinical significance based on CTCAE grading is defined as CTCAE grade 2 or higher with an increase of at least one CTCAE grade from baseline, please refer to Section
9.2. for further details. If the baseline value is missing, all post-baseline values with CTCAE

grade 2 or higher will be classified as possibly clinically significant. For the laboratory parameters recorded that do not have a CTCAE grading defined, the BI default rules for clinical significance should be applied (5).

Tumour lysis syndrome (TLS)

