7.8.1.2 Adverse events

Unless otherwise specified, adverse events analysis will be performed for on-treatment periods. Selected analyses (e.g. summary of AEs) will be repeated for the MTD evaluation period.

The analyses of AEs will be descriptive in nature and will follow the standard procedure laid down in the DM & SM (including all required tables and listings; guideline _'Handling and Summarization of AE Data for CTR and Integrated Summaries' (4). AEs will be coded with the most recent version of Medical Dictionary for Regulatory Activities (MedDRA). The version number will be displayed as a footnote in the respective tables and listings.

The system organ classes will be sorted alphabetically. In tables displaying AEs by dose cohort preferred terms will be sorted by descending frequency of adverse events in the "Total" BI 836826 group.

Each patient can be observed during the trial under several doses. Analysing the AE of all treatment courses will be carried out under the initial treatment. No formal statistical analysis is planned for the safety comparison.

The analysis of AEs will be based on the concept of treatment emergent AEs. That means that all adverse events occurring between first administration of BI 836826 until 6 weeks after last administration of BI 836826 will be assigned to the on-treatment period. All adverse events occurring before first administration of BI 836826 will be assigned to "Screening" and all adverse events occurring after last administration of BI 836826 + 6 weeks will be assigned to "post-study (for listings only). The actual planned dosage of BI 836826 administered on the day each AE starts will also be derived and will be included in the listing. Listings of screening events will not be sorted by initial treatment. Post-study listings will be sorted by initial treatment. For details on the treatment definition please refer to Section 6.1.

According to the BI standards, multiple recordings of AEs will be collapsed to episodes on the lowest level term and multiple episodes will be condensed to records on the PT and system organ class (SOC) level. CTCAE grade will be an additional criterion for collapsing and condensing AEs. The maximum CTCAE grade will be assigned to episodes and records. CTCAE grade and DLT information will be displayed in AE listings. MedDRA levels for condensing will be SOC and PT.

An overall summary of adverse events will be presented.

Reporting of CTCAE grades

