CTCAE grading within AE tables is displayed as "all grades", "Grade 1/2", "Grade 3/4" and "Grade 5". AEs with missing CTCAE or CTCAE grades not equal to 1 to 5 will be displayed under the category "all grades", but no category "missing grade" is displayed. A footnote is explaining that AEs with missing CTCAE or CTCAE grades not equal to 1 to 5 will be displayed under the category "all grades" and therefore the categories "Grade 1/2", "Grade 3/4" and "Grade 5" might not sum up to the category "all grades". A separate table will show

AEs leading to death. In this table no CTCAE grades will be shown. In the appendix (Section 16.1.9.2), the categorization "all Grades", "missing Grade", "Grade 1", "Grade 2", "Grade 3", "Grade 4" and "Grade 5" are used, but the "missing grade" column should only be displayed in case AEs with a missing CTCAE grade occured.

AE attributes "CTCAE Grade 1/2", "CTCAE Grade 3/4" and "CTCAE Grade 5" combined with drug relationship will be derived to avoid incorrect condensing. Consider, for instance, a patient with coincident drug-related abdominal pain with CTCAE Grade 1, and non-related vomiting with CTCAE Grade 3. Without the new attribute these AEs would be reported as drug-related Grade 3/4 under the SOC Gastrointestinal Disorder. With the new AE attribute these AEs would be excluded.

Additional AE attributes "Drug relationship combined with seriousness of the AE" and "Drug relationship combined with seriousness of the AE and CTCAE grade" is needed similarly to the AE attribute "CTCAE Grade 1/2", "CTCAE Grade 3/4" and "CTCAE Grade 5" combined with drug relationship respectively, as described above.

Frequencies of patients with AEs will be summarised by treatment, highest CTCAE grade, primary SOC and PT. Tables will be provided for patients with AEs of incidence > 10%, with drug-related AEs, with serious AEs (SAEs), with drug-related SAEs, with AEs leading to treatment discontinuation, with AEs leading to dose reduction, with protocol-specified significant AEs, with AEs leading to death, and with infusion-related reactions (IRRs).

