For Uric Acid and Hypokalemia, the CTCAE grade cannot always be assigned by the laboratory parameter itself as two different CTCAE grades have the same laboratory constellation, but are distinguished by additional clinical parameter. In this case a CTCAE grade of -1 will be assigned initially. Patients with a CTCAE grade of -1 will be treated as

- Grade 1 for Uric Acid
- Grade 1 for Hypokalemia

for all analyses. In laboratory listings, the CTCAE grade will be displayed as -1.

Patients with hepatic enzyme elevation will be tabulated. With respect to neutropenia, thrombocytopenia and leukopenia episodes the number of episodes and mean and median duration will be displayed. Additionally, laboratory values of special interest as described in Section 5.4.5 will be analyzed.

Additionally, a frequency table displaying number of patients with episodes of grade 4 neutropenia and concomitant AEs in the user-defined AE category (UDAEC) of any grade and grade 3/4 will be provided. In this context, concomitant AE is defined as AE with onset date within the neutropenia episode. The same table will be done for grade 3/4 episodes of neutropenia and concomitant AEs in the UDAEC of any grade and grade 3/4 will be done. The same applies for the display of patients with thrombocytopenia and bleeding events. For the definitions of neutropenia, thrombocytopenia and leukopenia episodes please refer to Section 5.2.5.2.

The prioritized laboratory values (see Section 5.4.5) will be displayed in Section 15 of the final CTR while all other laboratory parameters will be displayed in the Appendix of the CTR.

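### The SAP's cytopenia cross-tables have no place for grade 5, so a patient whose only severe concomitant event was fatal is missing from the severe column

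*SAP*

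**What the plan says.** SAP 7.8.2 (Laboratory data) plans a frequency table of patients with grade 4 neutropenia episodes, in which "concomitant AEs in the user-defined AE category (UDAEC) of any grade and grade 3/4 will be provided". It then adds a second version: "The same table will be done for grade 3/4 episodes of neutropenia and concomitant AEs in the UDAEC of any grade and grade 3/4". For platelets it says: "The same applies for the display of patients with thrombocytopenia and bleeding events". An event belongs in the neutropenia tables by its start date: "concomitant AE is defined as AE with onset date within the neutropenia episode". Fatal events are not excluded, and neither a grade 5 column nor a grade 3 or higher column is mentioned.

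Three other places bear on how these columns are read:

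- SAP 7.8.1.2 sets the grade categories for AE tables: "CTCAE grading within AE tables is displayed as 'all grades', 'Grade 1/2', 'Grade 3/4' and 'Grade 5".
- The same section says of collapsed and condensed AEs: "The maximum CTCAE grade will be assigned to episodes and records".
- SAP 5.4.5.2 has a rule for an episode that starts before the end-of-treatment visit and has not resolved: if "the patient dies, the end of the episode is defined by the date of death".

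**The concern.** A table that pairs severe cytopenia with its clinical complications is read mainly for its severe column. If that column stops at grade 4, the worst outcome is left out of it. The count then moves the wrong way: a complication that goes from grade 4 to fatal lowers the severe count by one patient.

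The setting makes this worth correcting. SAP 7 presents safety displays by dose cohort, and the dose-escalation cohorts have one, three or six patients, so a single misplaced patient is visible. Protocol 5.2.1.1 counts some complicated cytopenias as dose-limiting and says haematological events will be weighed when the dose for further development is defined. In the supplied text, no other planned table ties AEs to the cytopenia episode in which they began.

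**Working it through.** The documents give no figure to reproduce, so the check is to classify each possible worst grade under the columns as written.

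**Inputs.** The columns of the cross-tables come from SAP 7.8.2. The grade categories come from SAP 7.8.1.2. The grade carried by an event is its maximum, also from SAP 7.8.1.2.

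**Does grade 3/4 include grade 5 in this SAP?** SAP 7.8.1.2 lists the two as separate categories. SAP 7.8.1.3 specifies grade 3 or higher for infusion-related reactions, so the SAP has a wording for including fatal events when it wants them. No rule adds grade 5 to grade 3/4 in the cross-tables.

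**Classification of one patient by the worst grade of the concomitant event** (1 = counted, 0 = not counted):

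| Worst grade | Any grade (7.8.2) | Grade 3/4 (7.8.2) | Grade 5 (7.8.1.2) | Grade 3 or higher |
|---|---|---|---|---|
| 1 | 1 | 0 | 0 | 0 |
| 2 | 1 | 0 | 0 | 0 |
| 3 | 1 | 1 | 0 | 1 |
| 4 | 1 | 1 | 0 | 1 |
| 5 | 1 | 0 | 1 | 1 |

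Under the two columns of SAP 7.8.2, grade 5 falls in the same cells as grades 1 and 2.

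**Invented illustration: ten patients with a concomitant event.**

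- Set A, worst grades 1, 1, 1, 2, 2, 2, 2, 3, 3, 4: any grade = 10; grade 3/4 = 2 + 1 = 3.
- Set B, one grade 1 patient replaced by a grade 5 patient: any grade = 10; grade 3/4 = 2 + 1 = 3. The planned table is unchanged. With the missing columns, grade 5 = 1 and grade 3 or higher = 2 + 1 + 1 = 4.
- Set C, the grade 4 patient of set A replaced by a grade 5 patient: any grade = 10; grade 3/4 = 2. The severe count drops from 3 to 2 although the outcome is worse. Grade 3 or higher stays at 2 + 1 = 3.

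Subtracting grade 3/4 from any grade does not recover the mild events. The remainder contains grades 1, 2 and 5 and, if these tables follow the SAP 7.8.1.2 convention, events with no grade.

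**Do other outputs supply the link?** Fatal events appear in the AE tables with a Grade 5 category and in the table of AEs leading to death (both SAP 7.8.1.2). They also appear in the user-defined-category table by worst grade (SAP 7.8.1.4) and in the AE listings, which show the grade. None of these is described as limited to events starting within a cytopenia episode. A reader would have to match AE records to laboratory episodes patient by patient.

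**No percentage.** The number of fatal cases is not in the documents. SAP 7 takes the denominator of a subcategory from its main category, so the base could be patients with an episode and not the whole cohort.

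**The case against.** The strongest reply is that this is one supplementary descriptive display and that no safety information disappears. That is correct. A reader might infer that fatal complications vanish from the report; the documents do not support this, because the outputs listed above still show them. The user-defined-category table by worst grade comes closest, and in a trial of about 60 patients the link to an episode can be rebuilt from listings. What it lacks is the link to the episode, which is the purpose of the cross-tables.

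The mechanism can also be questioned. The maximum-grade rule and the grade categories are stated for AE analysis, while the cross-tables sit in the laboratory section, which does not say whether each patient is counted once at the worst grade. If counting is by event, a patient with a fatal event and a separate grade 3 or 4 event in the same category and episode could still appear as severe. This narrows the problem to patients whose only severe event was fatal; they drop out under either counting rule.

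It is tempting to describe the neutropenia table as one of infections. Bleeding is named for thrombocytopenia, but the neutropenia category is not named in the supplied text, so infection is an inference. The gap exists whatever the category is.

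The rule that ends an episode at death should not be read as a forecast of fatal complications. It covers death from any cause and shows only that death within an episode was considered possible.

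**Conclusion.** The point stands as a misleading display. As written, the severe column of the neutropenia and thrombocytopenia cross-tables omits any patient whose only severe concomitant event was fatal, and within those tables that patient cannot be told from one with a mild event. The size is one patient per such case. The number of cases is unknown and may be zero.

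This rests on one assumption: that grade 3/4 in SAP 7.8.2 means what it means in SAP 7.8.1.2. Nothing in the supplied text says otherwise.

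A reader might go further and conclude that dose selection is biased. The documents do not support that. Escalation and the expansion dose rest on review by the sponsor, the Coordinating Investigator and the DSMB (Protocol 3.1, 4.1.3 and 5.2.1.1), and nothing says these tables drive the choice. The MTD rule is unaffected. The observation that no other table makes this link applies only to the supplied text, because parts of the SAP are not public.

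**What to change.** In SAP 7.8.2, specify the concomitant-AE columns as any grade, grade 3 or higher, and grade 5, in place of any grade and grade 3/4. Alternatively, keep grade 3/4 and add a Grade 5 column, as the AE tables of SAP 7.8.1.2 already have. Apply the change to both neutropenia tables (grade 4 episodes and grade 3/4 episodes) and to the thrombocytopenia and bleeding displays. In the same edit, state whether each patient is counted once at the worst grade.

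The cost is a line or two of wording and one extra column per table. No new data are needed and no other analysis changes.

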#### 5.2.3 Assessment of safety laboratory parameters

5.2.3.1 General safety laboratory parameters

Blood samples and urine have to be collected at the time points specified in the Flow Chart. Blood samples should be collected more frequently in case of relevant toxicities; e.g. in case of grade 4 neutropenia or thrombocytopenia, to document as accurately as possible the duration of the AE. Safety laboratory examinations will include haematology, biochemistry, coagulation and qualitative urine analysis:

Haematology	Haemoglobin, red blood cell count (RBC), white blood cell count (WBC) with differential, platelets (PLT)
	Reticulocytes have to be measured only at Screening, Visit 1, Day 1 of each treatment course, at the EOT visit and during follow-up.
Biochemistry	Glucose, sodium, potassium, calcium, inorganic phosphate, creatinine, aspartate amino transferase (AST), alanine amino transferase (ALT), alkaline phosphatase (AP), lactate dehydrogenase (LDH), total bilirubin (if elevated provide direct bilirubin), urea, total protein, albumin, uric acid
	Serum immunoglobulin levels (IgG, IgM, IgA), direct antiglobulin test have to be measured only at Screening, Visit 1, Day 1 of each treatment course, at the EOT visit and during follow-up.
Coagulation	Activated partial thromboplastin time (aPTT), prothrombin time (PT), international normalised ratio (INR) where indicated (e.g. treatment with vitamin K antagonists)
Urine	pH, glucose, erythrocytes, leukocytes, protein, nitrite will be analysed by dipstick and reported as semiquantitative measurements. In case of pathological findings, further evaluation should be performed and results documented.
Pregnancy test	A serum pregnancy test needs to be obtained at the time points indicated in the Flow Chart in patients of childbearing potential.

In case a treatment course is delayed due to an adverse event, the patient should visit the site at least once a week for assessment of safety laboratory and adverse events. More frequent visits may be appropriate as assessed by the investigator.

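### The SAP's cytopenia co-occurrence tables leave out adverse events that began before the first low count, even when the event is still ongoing at that count

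*SAP*

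**What the plan says.** SAP 5.4.5.2 defines the episode from laboratory samples: "An episode of e.g. low neutrophils starts with the first occurrence of a CTCAE grade" of 3 or higher, and it "lasts until the first time the CTCAE grade falls back to" 2 or lower. For long episodes it adds: "If the episode starts before EOT and lasts during Follow-up the episode is censored with the date of DBL".

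SAP 7.8.2 then plans frequency tables of patients with grade 4 neutropenia episodes, and with grade 3/4 episodes, in which "concomitant AEs in the user-defined AE category (UDAEC) of any grade and grade 3/4 will be provided". An AE qualifies by its onset date alone: "concomitant AE is defined as AE with onset date within the neutropenia episode". For platelets, "The same applies for the display of patients with thrombocytopenia and bleeding events". There is no look-back before the first low sample, and no rule for an AE already ongoing at that sample.

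Blood counts are planned at every visit (Protocol 5.1.2.3 and Flow Charts). These are days 1, 2, 3, 4 and 8 of course 1, and days 1, 2, 3 (+2) and 8 (+2) of later 14-day courses. The end-of-treatment (EOT) visit is 14 (±2) days after the last administration. Protocol 5.2.3.1 adds: "Blood samples should be collected more frequently in case of relevant toxicities".

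**The concern.** The episode start is the date on which the low count was found, not the date on which the count fell. An AE that starts in a sampling gap, while the patient is already cytopenic, has an onset before the episode as defined.

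Take a patient with a normal neutrophil count on day 8, an AE with onset on day 12, and a grade 4 count on day 13. The AE may still be ongoing on day 13, but the table shows grade 4 neutropenia without a concomitant event.

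These are the only readable tables that pair a cytopenia episode with a clinical event in the same patient, and separate AE and laboratory summaries do not restore the pairing. Protocol 5.2.1.1 says that haematological AEs will be considered in defining the dose for further development. Escalation cohorts hold one to six patients, so a single misclassified patient can turn 1/6 into 0/6.

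**Working it through.** The plan gives no figure for this point, so there is nothing to reproduce. The check uses the nominal visit days. True episode length, the timing of the fall and the timing of the AE are assumptions.

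**1. Sampling gaps**
- Course 1: 1, 1, 1, 4, 7 days (days 1, 2, 3, 4, 8, 15).
- Later courses: 1, 1, 5, 7 days (days 1, 2, 3, 8, then day 1 of the next course or EOT).
- Stopping after course 1 with the second dose on day 2: EOT is at day 2 + 14 = day 16, so the last gap is 16 − 8 = 8 days.

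**2. Missed share if the fall is equally likely on any day**

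The rule compares dates, so the calculation uses whole dates, and a low sample on the AE onset date counts as captured. In a gap of g days the delay from fall to first low sample is g−1, …, 1, 0, which sums to g(g−1)/2. If AE onset is uniform over the d dates of the true episode, the share missed is the mean delay divided by d.

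Four courses, days 1 to 57:
- Course 1: 0+0+0+6+21 = 27.
- Courses 2 to 4: 0+0+10+21 = 31 each, so 93.
- Mean delay: 120/57 = 2.105 days.
- d = 7: 2.105/7 = 30%. d = 10: 21%. d = 14: 15%.
- d = 5: falls with a delay of 5 or 6 days are never detected (two in each of four 7-day gaps), leaving 57−8 = 49 onset days. The summed delay is (6+10) + 3×(10+10) = 76. Then 76/49 = 1.551, and 1.551/5 = 31%.

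One course, days 1 to 16, by the same steps:
- d = 5: (16/13)/5 = 25%. d = 7: (27/15)/7 = 26%.
- d = 10: (34/16)/10 = 21%. d = 14: (34/16)/14 = 15%.

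A simulation of both calendars gave the same values. Treating time as continuous gives 42%, 38%, 26% and 19% for four courses, but that counts same-date samples as late, which the rule does not do.

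**3. Missed share if the fall follows the infusion**

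| Timing of fall (four courses) | 5 d | 7 d | 10 d | 14 d |
|---|---|---|---|---|
| Any day, whole dates | 31% | 30% | 21% | 15% |
| Days 1–8 of a course, whole dates | 23% | 16% | 11% | 8% |
| Within 2 days of infusion, continuous time | 10% | 7% | 5% | 4% |
| Within 2 days of infusion, whole dates | 0% | 0% | 0% | 0% |

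Row 2: the delays over days 1–8 sum to 6 in course 1 and 10 in later courses. The mean is (6/8 + 3×10/8)/4 = 1.125 days, divided by d. Row 3: with daily samples the mean delay is 0.5 day, divided by d. Row 4: a planned sample falls on each of days 1, 2 and 3.

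**4. The other end of the episode**

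Recovery is also found late. In continuous time the mean lag to the next sample is Σg²/(2Σg) = (1+1+25+49)/28 = 2.71 days in later courses, and (1+1+1+16+49)/28 = 2.43 in course 1. AEs starting in that lag are counted although the patient has recovered.

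For a 7-day episode over eight courses, a simulation gives 38% missed. About 39% are added if AEs are as frequent after recovery as during cytopenia. If half of the AEs prompt a same-day low sample and the rate after recovery is a quarter of the rate during cytopenia, about 19% are missed and 10% added. Episodes carried to database lock widen the window further.

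**The case against.** The strongest reply is that the tables are supplementary and descriptive. Every on-treatment AE still appears in the AE and serious AE tables (SAP 7.8.1.2) and in the tables by user-defined category (SAP 7.8.1.4). The DLT criteria for febrile neutropenia and for thrombocytopenia with bleeding (Protocol 5.2.1.1) do not use the onset rule. Requiring onset inside a documented episode also has a rationale: an AE that predates any low count cannot be shown to follow from it. This stands, and it confines the point to the co-occurrence tables.

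Second, SAP 5.2.2 says that blood values change immediately after infusion, which is when sampling is densest. This also stands: with an early fall the loss is small or nil. The extra sampling in Protocol 5.2.3.1 helps too, but it follows recognition of a toxicity and cannot date an unrecognised fall.

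Third, the tables count patients. A patient with another AE starting inside an episode is still shown, so the patient-level loss may be smaller than the event-level shares above.

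A reader might infer more than the documents support:
- **That complications of cytopenia are under-reported in the trial.** They are not; only the pairing is affected.
- **That cytopenia is made to look more benign.** The late episode end works the other way. Full offset needs equal AE rates during and after cytopenia, and a lower rate after recovery is plausible, but no document gives these rates.
- **That an event which prompts the blood count is always lost.** It is captured if both fall on the same date.
- **That these tables decide the dose.** No section says so; escalation and expansion doses rest on review of all safety data and DLT-type events.
- **That the neutropenia table concerns infections.** The readable text names only a user-defined category.

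**Conclusion.** The point holds in a limited form. As written, the rule leaves AEs with onset before the first low sample out of the co-occurrence tables, including AEs still ongoing at that sample, while planned gaps reach 7 to 8 days. For true episodes of 5 to 14 days the loss is roughly 15 to 30% of co-occurring AEs if the fall is equally likely on any day, and about 0 to 10% if it comes within 2 days of infusion. Both ranges assume AE onset uniform within the true episode and no prompted samples. The tables can be wrong in both directions, and false additions after recovery do not restore the patients who were missed. The net direction is not established. This is a worthwhile, inexpensive improvement to secondary safety tables and does not affect the MTD analysis.

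**What to change.** Keep the existing count of AEs with onset inside the episode. Beside it, pre-specify a second column in SAP 7.8.2 that also includes:
- AEs ongoing on the date of the first low value;
- AEs with onset after the last sample of grade 2 or lower and before the first low value.

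In both cases, limit the look-back to 7 days before the first low value. Apply the column to neutropenia with the user-defined AE category and to thrombocytopenia with bleeding. Footnote that the episode end is sample-based, since the new column does not correct the late end. In the same edit, correct the pointer in SAP 7.8.2 from Section 5.2.5.2 to 5.4.5.2, where the episode definitions stand.

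The cost is a few lines of SAP text and one derived variable. AE onset and end dates are already collected (Protocol 5.2.2.2), so no new data are needed. The downside is that some AEs that began before the true fall will be included; the cap limits this and the side-by-side display makes it visible.
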